## **2.8 Safety analyses**

Summaries may be performed separately for initial (Week 1-16) period and entire treatment period (including follow-up). Week 16 is chosen due to the fact that placebo patients may be rescued as early as week 16. Use of data up to and including the last visit before rescue provides an unbiased comparison between AIN and placebo; data collected beyond week 16 are included in analyses which summarize the entire treatment period.

Safety analyses will be performed on treatment received (or actual treatment) as described below:

The actual treatment or treatment received for summaries of safety data will differ to the treatment assigned at randomization only if a subject received the wrong treatment during the entire study.

For those subjects who received not the treatment randomized, i.e. who received erroneously the wrong treatment at least once, an additional AE listing will be prepared displaying which events occurred after the treatment errors.

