### **1.1 Study design**

This multicenter study uses a randomized, double-blind, placebo-controlled, parallel-group design. A screening period (SCR) running up to 10 weeks before randomization will be used to assess subject eligibility followed by 104 weeks of treatment.

At BSL approximately 990 subjects whose eligibility is confirmed will be randomized to one of four treatment groups in 2:2:2:3 ratio:

- Group 1 - secukinumab 150 mg s.c. without loading regimen
- Group 2 - secukinumab 150 mg s.c. with loading dose regimen
- Group 3 - secukinumab 300 mg s.c. with loading dose regimen
- Group 4 - Placebo s.c.

Subjects in Group 4 (Placebo) will be randomized (1:1) at BSL to two different treatment sequences:

Placebo s.c. till Week 16/24 followed by secukinumab 150 mg s.c. every 4 weeks starting at Week 16/24.

Placebo s.c. till Week 16/24 followed by secukinumab 300 mg s.c. every 4 weeks starting at Week 16/24.

**At randomization**, subjects will be stratified on the basis of previous anti-TNF therapy as TNF $\alpha$  inhibitor naïve (TNF-naïve) or TNF $\alpha$  inhibitor inadequate responders (TNF-IR).

At each study treatment visit, one (for secukinumab 150 mg) or two (for secukinumab 300 mg) s.c. injections in the form of PFS will be administered, since secukinumab is available in 1.0 mL (150 mg) PFSs. Placebo to secukinumab is also available in 1.0 mL to match the active drug.

**At Week 16**, subjects who have been randomized to secukinumab groups at BSL (Groups 1-3) will be classified as either responders ( $\geq 20\%$  improvement from BSL in both tender joint count (TJC) and swollen joint counts (SJC)) or non-responders ( $< 20\%$  improvement from BSL TJC or SJC), however, they will continue on the same treatment irrespective of their response status.

**At Week 16**, subjects who have been randomized to placebo at BSL (Group 4) will be classified as either responders ( $\geq 20\%$  improvement from BSL in both TJC and SJC) or non-responders ( $< 20\%$  improvement from BSL TJC or SJC):

- Subjects who are **non-responders** will receive either secukinumab 150 mg or 300 mg s.c. every 4 weeks starting at Week 16 (as dictated by treatment sequence assigned to these subjects at BSL).

- Subjects who are **responders** will continue to receive placebo every 4 weeks. At Week 24, these subjects will receive either secukinumab 150 mg s.c. or 300 mg s.c. every 4 weeks. (as dictated by treatment sequence assigned to these subjects at BSL).

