## **2.2 Analysis sets and treatment groups**

The following analysis sets will be used for the data analysis.

**Randomized set:** The randomized set will be defined as all subjects who were randomized. Unless otherwise specified, mis-randomized subjects (mis-randomized in Interactive Voice Response (IVR)) will be excluded from the randomized set.

Mis-randomized subjects are defined as those subjects who were mistakenly randomized into the IVR prior to the site confirming all eligibility criteria had been met and to whom no study medication was given. Mis-randomized patients are treated as screen failures.

**Full analysis set (FAS):** The FAS will be comprised of all subjects from the randomized set to whom study treatment has been assigned. Following the intent-to-treat principle, subjects will be analyzed according to the treatment assigned to at randomization, but actual anti-TNF status.

**Dactylitis subset:** The dactylitis subset will include all FAS subjects who have dactylitis at baseline.

**Enthesitis subset:** The enthesitis subset will include all FAS subjects who have enthesitis at baseline.

**Psoriasis subset:** The psoriasis subset will include all FAS subject who have  $\geq 3\%$  of the body surface area (BSA) affected by psoriatic skin involvement at baseline.

**Nail subset:** The nail subset will include all FAS subject who have psoriasis currently in nails at baseline.

**Up-titration subset:** Up-titration subset will include all FAS subjects who have been up-titrated to secukinumab 300mg in the second year of the study.

**Safety set:** The safety set includes all subjects who took at least one dose of study treatment during the treatment period. Subjects will be evaluated according to treatment received.

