## **2.4 Treatments (study treatment, rescue medication, concomitant therapies, compliance)**

### **2.4.1 Study treatment / compliance**

The analysis of study treatment data will be based on the safety set. The duration of exposure to study treatment will also be summarized by treatment group. In addition, the number and percentage of subjects with cumulative exposure levels (e.g. any exposure,  $\geq 1$  week,  $\geq 2$  weeks,  $\geq 3$  weeks,  $\geq 4$  weeks,  $\geq 8$  weeks, etc.) will be presented.

Duration of exposure of a treatment will be defined as the time from first dose of the treatment to the time of treatment switch (for subjects who switch treatment) or minimum of (last dose of the treatment + 84 days) and (last visit date). Patients who switch treatment during the study (e.g. from placebo to active treatment or between active treatment groups) will have exposure to both medications/doses using the appropriate start and stop dates.

Duration of exposure (years) = duration of exposure (days) / 365.25

Duration of exposure (100 subject years) = duration of exposure (years) / 100

The analyses of duration of exposure described above will be done for the entire study treatment period.

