## **3 Sample size calculation**

A 5% two-sided type I error rate will be used to control for type I error. Three secukinumab regimens will be tested versus placebo with respect to the primary endpoint (ACR20 response at Week 24), thus the type-I-error will be split to 1.67% two-sided for each comparison. Sample sizes will be based on this type I error assumption. With an assumed placebo rate of 15% and secukinumab 51% (FUTURE 2), the study is over 99% powered to detect a treatment difference of ACR20 in the FAS population, assuming 220 subjects in a secukinumab treatment group, and 330 subjects in the placebo group (Fisher's exact test, nQuery 7.0). This power is applicable for all three dose regimens, as the sample size is driven by structural endpoint.

Power for secondary variables was calculated using a two-sided 1.67% type I error. With an assumed placebo rate of 7% and secukinumab 35% (FUTURE 2), the study is over 99% powered to detect a treatment difference of ACR50 in the full FAS population, assuming 220 subjects in a secukinumab treatment group, and 330 subjects in the placebo group (Fisher's exact test, nQuery 7.0).

For structural endpoint, historical data (FUTURE 1) showed a standard deviation of 1.132 on active treatment and 2.435 on placebo at Week 24, and a difference of 0.52. Using the above assumptions, there is 83% power to show statistically significant differences assuming 220 subjects in a secukinumab group and 330 subjects in the placebo group (Satterthwaite t-test, nQuery 7.0).

A standard deviation of approximately 0.49 and a treatment difference of 0.17 has been observed for the change from baseline at Week 24 in HAQ-DI® (FUTURE 2). Using those assumptions, the study has approximately 94% power to detect a difference between secukinumab and placebo (Two group t-test, nQuery Advisor 7.0), assuming 220 subjects in a secukinumab treatment group and 330 subjects in the placebo group.

For the presence of dactylitis at Week 24 in the subset of subject who have dactylitis at BSL, with an assumed placebo rate of 85% and secukinumab 50% (FUTURE 2), there is about 99% power to show statistically significant difference between secukinumab (110) and placebo (165 subjects), assuming 50% subject have dactylitis at BSL (Fisher's exact test, nQuery 7.0).

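### SAP 2.8 reassigns actual treatment only for a whole-study error, which does not fit a design with a planned placebo switch; the rule should apply per analysis period

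*SAP*

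**What the plan says.** For the safety set, SAP 2.2 says "Subjects will be evaluated according to treatment received", and Protocol 9.1 says the same. Neither place defines treatment received for a subject with dosing errors.

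SAP 2.8 supplies the definition: actual treatment "will differ to the treatment assigned at randomization only if a subject received the wrong treatment during the entire study". For subjects wrongly treated at least once, "an additional AE listing will be prepared displaying which events occurred after the treatment errors". No other provision is made for partial errors.

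SAP 1.1 describes the placebo sequences, for example "Placebo s.c. till Week 16/24 followed by secukinumab 150 mg s.c. every 4 weeks starting at Week 16/24"; the other sequence leads to 300 mg.

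SAP Table 2-1 plans crude incidence of AEs and SAEs for Day 1 to Week 8. For Day 1 to Week 16 it plans crude incidence of all the listed safety endpoints. Of data before rescue, SAP 2.8 says: "Use of data up to and including the last visit before rescue provides an unbiased comparison between AIN and placebo". Section 2.8 says that separate period summaries may be performed, while the sentence introducing Table 2-1 says that its analyses will be.

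**The concern.** A rule that keeps the randomised label unless every dose was wrong is a common convention where treatment is fixed for the whole study. Here the assigned treatment of the placebo group changes at Week 16 or 24, but the condition is still judged over the whole study. A subject can then have had no placebo dose at all in the period being summarised and still be counted under placebo, because later doses were as assigned.

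At stake is the placebo-controlled part of the safety evaluation. Active-treatment events could sit in the control column, and whether they do depends on what happened to the subject after the period. The extra listing shows such events but leaves the numerators and denominators of the incidence tables unchanged.

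**Working it through.** The SAP gives no figure for this point, so the check is mainly a reading of the rule against the design.

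**Applying the rule.** Doses before Week 16 fall at baseline and Weeks 1, 2, 3, 4, 8 and 12, which is seven doses (Protocol 3.1 and Table 6-1). Take two subjects randomised to placebo, both given secukinumab in error at all seven.

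- Subject A continues and is dosed as assigned from the planned switch. The error did not last the whole study, so A stays under placebo.
- Subject B stops before any correct dose. Every dose was wrong, so B is moved to secukinumab.

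Their dosing to Week 16 is identical, yet they fall in different columns of the Day 1 to Week 16 table. The difference comes from later continuation, which may itself follow an adverse event.

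**Applying it at a lock.** SAP 4.1.2 sets Week 24 and Week 52 cut-offs, when most subjects are still being treated. For a subject wrong at every dose so far, the whole-study condition is not yet known. If the subject is moved and later dosed as assigned, the same Week 16 table changes at the next lock. The SAP does not say how to apply the condition at these locks.

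**Looking for another provision that repairs it.**

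- SAP 2.1 says treatment groups may differ by period and refers to 2.2.2. That section lists only randomised treatment and treatment sequence, with no rule for misdosing.
- SAP 2.4.1 says subjects who switch "will have exposure to both medications/doses using the appropriate start and stop dates", but this is for the entire treatment period. Table 4-3 illustrates exposure-adjusted rates, which Table 2-1 reserves for the entire period. Neither moves a subject in a crude-incidence table to Week 8 or Week 16.
- The AE listing moves nobody.

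**Size.** The planned group sizes come from SAP 3: "assuming 220 subjects in a secukinumab treatment group, and 330 subjects in the placebo group". They agree with 990 subjects at 2:2:2:3, since 990 × 3/9 = 330 and 990 × 2/9 = 220.

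Let k misdosed subjects remain among 330 in the placebo column. Let p1 be the event probability on secukinumab and p0 that on placebo.

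- Misclassified share = k/330.
- Expected placebo incidence = p0 + (k/330)(p1 − p0), so the largest possible shift is k/330.
- Expected risk difference = (1 − k/330)(p1 − p0).

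The documents give no error count, so k is an assumption:

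| k (assumed) | Share of column | Largest shift in placebo incidence | Fraction of risk difference kept |
|---|---|---|---|
| 1 | 0.30% | 0.30 points | 0.9970 |
| 3 | 0.91% | 0.91 points | 0.9909 |
| 10 | 3.03% | 3.03 points | 0.9697 |

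**The case against.** The strongest reply is that SAP 2.8 is an operational definition of treatment received. How much wrong treatment should trigger a move (all doses, most or any) is a convention, and a strict one protects the randomised comparison. That stands. A reader might infer that 2.8 flatly contradicts SAP 2.2 and Protocol 9.1, but those sections leave the term undefined and 2.8 defines it. What remains is that the definition fits this design badly.

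It can also be said that the scenario is remote. It needs seven consecutive errors with kits assigned through IRT, followed by correct dosing. This stands too, and no frequency is documented. A reader might further infer that the condition can almost never be met in the placebo group. That is not shown: Subject B above meets it, and if the wrong treatment is read at the level of the assigned sequence, others might.

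Partial errors are already visible, because the listing covers anyone wrongly treated even once and SAP 2.3.1 tabulates protocol deviations. Visibility is useful, but it does not correct a table.

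A stricter remedy is tempting: move a placebo subject to secukinumab from the first erroneous active dose. The objection to that is sound. It treats the arms asymmetrically, can put one person in two columns of a crude-incidence table with no denominator rule, and reclassifies on post-randomisation events. It is not recommended.

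**Conclusion.** The point holds in a limited form. By its wording, SAP 2.8 keeps a placebo subject who received only secukinumab to Week 16, and was then dosed as assigned, in the placebo column to Week 8 and Week 16. The rule also cannot be settled for ongoing subjects at the Week 24 and Week 52 locks.

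The expected effect is small, at 0.3% of the placebo column per subject. This rests on the planned 330 placebo subjects and an unknown error count. It is unlikely to matter for common events, though for a rare event one misplaced case can be noticed.

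Three stronger readings are not supported. The rule does not always hide a drug effect: the pull toward no difference is an expectation, and a misdosed subject without the event adds nothing to the placebo numerator. It does not distort exposure denominators in the early comparison, because those tables are crude incidences. And Day 1 to Week 16 is not the only placebo comparison, since Day 1 to Week 8 is also planned. The case for a change is that the rule and the design do not match and the repair is nearly free, not that a large bias is expected.

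**What to change.** In SAP 2.8, replace the whole-study condition with the analysis period. Actual treatment differs from randomised treatment in a given period if the subject received only the wrong treatment throughout that period, for example at every dose before the planned Week 16 or Week 24 switch. The subject is then counted under the regimen actually received, and the text should say which secukinumab column that is. The same rule applies in both directions, so a secukinumab subject given only placebo in the period is handled alike. For partial errors, keep the randomised column and the planned AE listing. A cross-reference from SAP 2.2 would make clear that 2.8 defines treatment received.

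This also settles the rule at the locks, since the doses in a completed period are known by then. It is best agreed before the Week 24 lock, after which the sponsor's team is unblinded (Protocol 3.5).

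The cost is one or two sentences and one derivation. Administration dates are in the Dosage Administration Record eCRF (Protocol 6.3) and assigned kits are in the IRT (Protocol 5.5.4), so no new data are needed. The downside is that a rare subject may appear in one column for an early period and another for a longer one, which a footnote can explain.

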### **2.8.1 Adverse events (AEs)**

The crude incidence of treatment emergent adverse events (AEs) (i.e. events started after the first dose of study treatment or events present prior to the first dose of study treatment but increased in severity based on preferred term and on or before last dose + 84 days) will be summarized by primary system organ class and preferred term. Confidence intervals for the crude rate will be derived as described in [Section 4.2.4.1](#) In addition, exposure time-adjusted rates (incidence rate) including 95% confidence intervals will be provided for the entire treatment period (see [Section 4.2.5.1](#)) to adjust for differences in exposure. Graphical displays of the crude incidence rates and exposure-adjusted rates will be presented for all AEs and serious AEs by system organ class.

Adverse events reported will be presented in descending frequency according to its incidence in total secukinumab group (combining all secukinumab treatment groups) starting from the most common event. Summaries (crude incidences only) will also be presented for AEs by severity and for study treatment related AEs. If a particular AE 'severity' is missing, this variable will be listed as missing and treated as missing in summaries. If a subject reported more than one adverse event with the same preferred term, the adverse event with the greatest severity will be presented. If a subject reported more than one adverse event within the same primary system organ class, the subject will be counted only once with the greatest severity at the system organ class level, where applicable.

Separate summaries will be provided for adverse events suspected to be related to study drug, deaths, serious adverse events, and adverse events leading to discontinuation and adverse events leading to temporary dose interruption.

Adverse events will also be reported separately by SMQ according to MedDRA. The MedDRA version used for reporting the study will be described in a footnote.

Non-treatment emergent adverse events will be listed.

Algorithms for date imputations will be provided in RAP M8.

For serious adverse events (SAEs) occurred during screening a listing will be prepared for all subjects screened including screening failures.

When adjudication is required of major cardiovascular events, a listing of those types of events as reported by the investigator and confirmed by adjudication will be provided.

The safety analyses that will be performed for treatment emergent AEs and on treatment labs, ECG and vital signs for each analysis period is described in [Table 2-1](#).

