## **2 Statistical methods**

### **2.1 Data analysis general information**

Summary statistics for continuous variables include N, mean, standard deviation, minimum, lower quartile, median, upper quartile, and maximum. For binary or discrete variables the absolute number of subjects in each category and relative frequencies will be provided.

Unless otherwise specified, p-values will be presented as 2-sided p-values and the type I error rate (alpha) will be 5%.

Inferential efficacy comparisons with placebo will generally focus on the first 16-weeks of treatment except for radiographic assessment which will focus on the first 24-weeks of treatment unless otherwise specified.

Efficacy and safety data for the placebo-controlled period (or the entire treatment period as appropriate) will be presented by randomized treatment groups. Subjects may be included in more than one treatment group for some analyses (e.g. exposure-adjusted AEs over the entire treatment period).

Note that the treatment groups for a subject may differ depending on the time period of the analysis and whether one assesses the subject for efficacy or safety (see [Section 2.2.2](#) for details).

Data may also be presented by a combination of the 'original' and 'switch' treatment groups. These treatment groups represent the treatment combinations the subjects experience over the course of the entire trial.

Subjects will receive treatment at BSL, Weeks 1, 2 and 3, followed by treatment every 4 weeks starting with Week 4 through Week 104 (with last dose at Week 100).

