**Table 2-1      Overview of analyses on some safety endpoints**

Analysis period	AEs & SAEs	AEs by severity	Study drug related AEs	AEs-SMQ	Risk	Notables for (vitals/ECG), lab criteria
Day 1 – Week 8	crude incidence					
Day 1 – Week 16	crude incidence	crude incidence	crude incidence	crude incidence	crude incidence	crude incidence
Entire Treatment	crude incidence	crude incidence	crude incidence	exposure time	crude incidence	crude incidence
	exposure time			adjusted incidence	exposure time	
	adjusted incidence*				adjusted incidence	

\*Exposure-adjusted incidence rates will be done for the following :

at the PSOC for AE and SAE and Level 1 for Risks and SMQ analyses

at the PT level for common AEs, which is defined as at least 2% of the patients in the combined AIN457 groups during the initial treatment period (i.e. up to week 24) or events that had an incidence rate of at least 5.0 cases per 100 subject-years in the combined AIN457 groups during the entire treatment period

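### Over the entire treatment period, AEs by severity, drug-related AEs and notable values are tabulated as crude incidence only, on unequal exposure and with undefined columns

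*SAP*

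**What the plan says.** SAP 2.8.1 plans crude incidence for treatment-emergent AEs. It adds that "exposure time-adjusted rates (incidence rate) including 95% confidence intervals will be provided for the entire treatment period", giving unequal exposure as the reason. Two outputs are then excepted: "Summaries (crude incidences only) will also be presented for AEs by severity and for study treatment related AEs".

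SAP Table 2-1 ("Overview of analyses on some safety endpoints") has the same pattern in its Entire Treatment row:

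- AEs and SAEs, and Risks: crude and exposure-adjusted incidence.
- SMQs: exposure-adjusted incidence.
- AEs by severity, drug-related AEs, and "Notables for (vitals/ECG), lab criteria": crude incidence only.

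The footnote places the adjusted rates "at the PSOC for AE and SAE and Level 1 for Risks and SMQ analyses", and at preferred-term level for common AEs. The Day 1 to Week 16 row gives crude incidence for every output.

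The columns of the entire-period tables are not fixed. SAP 2.1 says: "Efficacy and safety data for the placebo-controlled period (or the entire treatment period as appropriate) will be presented by randomized treatment groups". SAP 2.2.2 allows randomised treatment or treatment sequence, with the switch treatment optionally shown separately for some safety summaries. SAP 2.8 analyses safety by treatment received, but lets this differ from the randomised treatment only if the wrong treatment was given throughout the study. SAP 2.4.1 and Table 4-3 do split exposure at the switch, but they concern exposure duration and incidence rates, not crude tables.

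**The concern.** Unequal exposure, the SAP's own reason for adjusting, applies just as much to severe AEs, drug-related AEs and notable values, and the SAP does not explain why they are left out. A crude percentage rises with time at risk. A column covering 16 to 24 weeks and one covering up to 104 weeks would differ even if the drug did nothing. If the placebo column instead follows randomised subjects through the switch, most of its time is on secukinumab and a real difference is diluted. Severe and drug-related AEs are prominent safety outputs, and the entire-period table is where their long-term frequency will be read.

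**Working it through.** The documents give no event rate or expected incidence on this point, so there is no stated figure to reproduce. The check asks what crude incidence shows when both arms share the same constant event rate, that is, with no drug effect.

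**Inputs from the documents**

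- Placebo ends at Week 16 for non-responders and Week 24 for responders (Protocol 3.2). About 66% of placebo subjects are expected to be Week 16 non-responders (Protocol, Amendment 1 rationale, item 4).
- Secukinumab runs to Week 104, with the last dose at Week 100 (SAP 2.1).
- Dropout is 25% in the first year (Protocol section 4).
- Scheduled post-baseline laboratory draws (Protocol Tables 6-1 and 6-2): 7 to Week 16, 9 to Week 24, 22 to Week 104.

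**Assumptions**: dropout continues at the same rate in year 2; event rates are constant and varied over a range; laboratory visits are independent.

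**Exposure**

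- Without dropout: placebo 0.66×16 + 0.34×24 = 18.7 weeks; 104/18.72 = 5.6.
- With dropout, λ = −ln(0.75)/52 per week and mean exposure to week T is (1 − e^(−λT))/λ. This gives 17.7 weeks on placebo and 79.1 on secukinumab, ratio 4.5.

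**Crude incidence, placebo counted up to the switch**

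With 16-week risk p, the weekly rate is h = −ln(1 − p)/16. Crude incidence to week T is h/(h+λ) × (1 − e^(−(h+λ)T)), and λ = 0 gives the case without dropout. Placebo is weighted 0.66 at T = 16 and 0.34 at T = 24; secukinumab uses T = 104.

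| 16-week risk | Placebo, with dropout | Secukinumab, with dropout | Ratio | Ratio, no dropout |
|---|---|---|---|---|
| 0.5% | 0.55% | 2.4% | 4.4 | 5.5 |
| 1% | 1.1% | 4.8% | 4.4 | 5.4 |
| 5% | 5.5% | 21.9% | 4.0 | 4.9 |
| 10% | 11.0% | 38.9% | 3.5 | 4.3 |
| 20% | 21.7% | 62.2% | 2.9 | 3.3 |
| 30% | 32.3% | 75.7% | 2.4 | 2.7 |
| 60% | 62.3% | 91.1% | 1.5 | 1.5 |

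The exposure-adjusted rate is the same in both arms by construction. A 5% 16-week risk corresponds to 16.7 per 100 subject-years in each, ratio 1.0.

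**Laboratory notables**

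For a per-visit chance q, incidence is 1 − (1 − q)^visits. Expected placebo draws are 0.66×7 + 0.34×9 = 7.68. The ratio therefore cannot exceed 22/7.68 = 2.9 (22/9 = 2.4 to 22/7 = 3.1 at the two switch times). At q = 1% it is 7.4% against 19.8%, ratio 2.7. It is 2.1 at q = 5% and 1.2 at q = 20%. Nothing was computed for vital signs or ECG.

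Plain person-time adjustment does not repair this. Draws run at 7.68/18.72 = 0.41 per week on placebo and 22/104 = 0.21 per week over the full secukinumab period. A finding driven by the number of draws would then look about half as frequent on secukinumab (0.21/0.41 = 0.5).

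**Placebo column kept as randomised or by sequence**

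Planned follow-up is then about equal, but the column holds (104 − 18.72)/104 = 82% secukinumab time without dropout, or (79.1 − 17.7)/79.1 = 78% with it.

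**The case against.** The strongest reply is that the entire-period table is not the SAP's placebo comparison. Table 2-1 plans Day 1 to Week 16 crude tables for all three outputs. SAP 2.8 says "Use of data up to and including the last visit before rescue provides an unbiased comparison between AIN and placebo", while "data collected beyond week 16 are included in analyses which summarize the entire treatment period". This stands. A reader might infer that the plan has no valid placebo contrast for severe AEs, drug-related AEs or notables, and the documents do not support that. All AEs, SAEs, SMQs and Risks are also already exposure-adjusted over the full period.

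A reader might also infer that secukinumab rates will be several-fold higher by construction. That is too strong. It needs placebo tabulated on its time before the switch, whereas SAP 2.1 and 2.2.2 lean towards randomised or sequence columns, where the defect is contamination. Even on pre-switch time the ratio shrinks as events become common. Denser early monitoring on placebo lowers the laboratory ratio rather than raising it.

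A third inference, that up-titration to 300 mg confounds the crude dose comparison, is weak. SAP 2.2.2 separates subjects who stay on 150 mg from those up-titrated at the final lock, and SAP 2.4.1 defines exposure duration, not crude AE columns.

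What the reply leaves unanswered is why the entire-period tables for these outputs lack the adjustment given to the others, and what their columns contain. The Week 16 tables cannot describe long-term frequency.

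**Conclusion.** The point holds for the entire-period tables. On pre-switch placebo columns, crude incidence overstates the secukinumab-to-placebo ratio about 3.5 to 4.4 times for events with a 16-week risk up to 10%, less than 3 times once that risk exceeds roughly 20%, and at most about 3 times for laboratory notables. On randomised or sequence columns, the placebo figure rests on roughly four-fifths secukinumab time. Neither layout gives an interpretable crude contrast.

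The sizes rest on equal constant event rates, the expected 66% switch share, the stated 25% first-year dropout, the same rate assumed for year 2, and event risks that the documents do not give. The randomised comparison to Week 16 is unaffected. This should be corrected, but it concerns descriptive outputs. Adjusted rates remain descriptive too: the method in SAP 4.2.5.1 assumes a constant rate, and placebo time after Week 16 comes from responders only.

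**What to change.** In SAP Table 2-1, Entire Treatment row, and in SAP 2.8.1:

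1. Add exposure-adjusted incidence for AEs by severity and study-drug-related AEs, using SAP 4.2.5.1 with exposure split at the switch as in Table 4-3. Remove the restriction to crude incidence for that period.
2. State that the columns of these entire-period tables are by treatment received, with placebo time ending at the switch.
3. For notable laboratory, vital-sign and ECG values, do not use a single person-time rate as the placebo contrast. Limit that contrast to visit-matched data before the switch, and show later data by period.
4. Keep the Day 1 to Week 16 crude tables as the placebo comparison.

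The rate method is already specified, and Protocol 9.5.3 already provides for AE incidence per 100 subject-years where appropriate. No new data are needed. The cost is SAP wording and a few more table columns.
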